To explore a potential strategy to reduce the severity of PPES, Clobetasol 0.05% cream for first 12 weeks will be prophylactically applied to palms and soles of patients in arm A1 and (pre-emptive strategy). Patients in arm A2 and B2 will be treated per investigator discretion when they develop PPES (reactive strategy). All patients will be required to fill HFS14 quality of life questionnaire on C1D14, C2D1, C2D14, and C2D28 intervals.

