1.2 QOL Tools

- 1.21 QOL is an important outcome and covariate in this trial because the treatments are expected to differ in terms of their symptom profiles and impact on patient well-being. Previous data has indicated that the most prevalent QOL issues with these patients are fatigue, pain, weight loss, and other symptoms, as well as more general aspects of QOL such as ability to enjoy life and contentedness in QOL (Odom et. al. 2010). We hypothesize that patients receiving regorafenib will experience greater deficits in QOL as reflected by scores on the HSF14, the BFI and the LASA. These questionnaires have specific application to this population.

The HSF14 has been specifically designed to capture changes in QOL related to PPES. Cronbach's alpha for this questionnaire is 0.93. It involves 14 questions

with three domains: hand, feet, and social. The final score for this questionnaire ranges from 2-100, where a higher score indicates greater QOL impairment (Sibaud et. al., 2011). For comparison to other QOL questionnaires, the HSF14 will be converted to a 0-100 scale, where a higher score indicates better QOL.

The Brief Fatigue Inventory (BFI), a 9-item questionnaire, has been validated as a short and comprehensive instrument to assess severity of fatigue and fatigue-related impairment in cancer patients. The reliability estimated with Cronbach's alpha ranges from 0.82 to 0.97. Recently, both the German version and the Japanese version of the BFI has been validated with test-reliability (mean scores of 0.93) and impairment (mean scores of 0.87) for the German version and reliability with Cronbach's alpha at 0.96 for the Japanese version. Minor differences were seen in the validation of the German version compared to the original version.

Linear Analogue Self Assessment (LASA) items have been validated as general measures of global QOL dimensional constructs in numerous settings (Grunberg et al., 1996; Gudex et al, 1996; Hyland et al., 1996; Srivatanakul, 1983; Wewers, 1990). A series of LASA items have been constructed and validated at Mayo Clinic for use in cancer patients (Bretscher et al, 1999). These items have been seen to be important prognostic factors for cancer patient survival and should be included as covariates in survival analysis (Sloan, JCO, 2012).

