- 3.23 Congestive heart failure $>$ New York Heart Association (NYHA) class 2.
- 3.24 Unstable angina (angina symptoms at rest), new-onset angina (begun within the last 3 months) or myocardial infarction less than 6 months prior to randomization.
- 3.25 Cardiac arrhythmias requiring anti-arrhythmic therapy. Note: Pace makers, beta

blockers or digoxin are permitted.

- 3.26 Uncontrolled hypertension. (Systolic blood pressure > 140 mmHg or diastolic pressure > 90 mmHg despite optimal medical management).
- 3.27 History of or current pheochromocytoma.
- 3.28 Arterial or venous thrombotic or embolic events such as cerebrovascular accident (including transient ischemic attacks), deep vein thrombosis or pulmonary embolism ≤ 6 months prior to randomization.
- 3.29a Ongoing infection > grade 2 NCI-CTCAE version 4.0.
- 3.29b Known history of chronic hepatitis B or C.
- 3.29c Patients with seizure disorder requiring medication.
- 3.29d Symptomatic metastatic brain or meningeal tumors unless the patient is > 6 months from definitive therapy, has a negative imaging study within 4 weeks of randomization and is clinically stable with respect to the tumor at the time of randomization. Note: Patient must not be undergoing acute steroid therapy or taper (chronic steroid therapy is acceptable provided that the dose is stable for one month prior to and following screening radiographic studies).
- 3.29e History of organ allograft (including corneal transplant).
- 3.29f Evidence or history of bleeding diathesis or any hemorrhage or bleeding event >CTCAE grade 3 ≤ 4 weeks prior to randomization.
- 3.29g Non-healing wound, ulcer, or bone fracture.
- 3.29h Renal failure requiring hemo-or peritoneal dialysis.
- 3.29i Dehydration CTCAE (version 4.0) grade ≥ 1 .
- 3.29j Substance abuse, medical, psychological or social conditions that may interfere with the patient's participation in the study or evaluation of the study results.
- 3.29k Known hypersensitivity to any of the study drugs, study drug classes, or excipients in the formulation.
- 3.29l Interstitial lung disease with ongoing signs and symptoms at the time of informed consent.
- 3.29m Persistent proteinuria of CTC Grade 3 or higher (≥ 3.5 g/24 hrs).
- 3.29n Patients unable to swallow oral medications.
- 3.29o Any malabsorption condition.
- 3.29p Unresolved toxicity greater than CTCAE (version 4.0) Grade 1 attributed to any

prior therapy/procedure excluding alopecia and oxaliplatin induced neurotoxicity \leq Grade 2.

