4.0 Test Schedule

Tests and procedures	Active Monitoring Phase										
	≤7 days prior to randomization	Cycle 1 ¹³				Cycle 2 ¹³				After week 8: Every 4 weeks until progression (+/- 3 days)	At PD, withdrawal or removal
		Week 1 (Day 1)	Week 2 (Day 8)	Week 3 (Day 15)	Week 4 (Day 22)	Week 1 (Day 1)	Week 2 (Day 8)	Week 3 (Day 15)	Week 4 (Day 22)		
History and exam, weight, ECOG PS ¹² , blood pressure	X	X ¹²	X	X	X	X	X	X	X	X	X
Height	X										
Adverse event assessment ⁸	X		X	X	X	X	X	X	X	X	X
Hematology ^{8, 11} : CBC/ differential, ANC, INR/PTT ^{8, 10}	X	X				X				X	
Chemistry ^{8, 11} : SGOT (AST), alk phos, T. bili, serum creatinine, calcium, glucose, Na, K, SGPT (ALT)	X	X		X ⁷		X ⁷		X ⁷		X	
Albumin	X										
Urine proteinuria or urine protein creatinine ratio	X										
Tumor measurement ⁸ (CT scan of chest, abdomen and pelvis) (MRI if CT is not feasible)	X ¹								X ¹	X ¹	X ^{1,9}
ECG ⁶	X										
Serum pregnancy test	X ²										
Mandatory blood sample (see Section 14.0)	X ^{4,R}	(Day 7) X ^{4,R}	(Day 14) X ^{4,R}	(Day 21) X ^{4,R}		(Day 1) X ^{4,R}		(Day 21) X ^{4,R}			
Patient Medication Diary (Appendix II) ³		X	X	X	X	X	X	X	X	X	
Patient Questionnaire Booklets (Appendices IV, V, VI)	X ⁵		X ^{5,8}			X ^{5,8}	X ^{5,8}		X ^{5,8}		

1. CT scans preferred (MRI if CT is not feasible) of the chest, abdomen and pelvis. Use same imaging throughout the study. Tumor measurements at baseline (≤28 days prior to randomization) and every 8 weeks until progression.
2. For women of childbearing potential only.

3. The diary must begin the day the patient starts taking the medication and must be completed per protocol and returned to the treating institution weekly during Cycles 1 and 2 and every 4 weeks thereafter.
 4. Kits are required for this collection. Samples will be collected for PK analysis of C_{min} of regorafenib, M2 and M5 at the following time points: Cycle 1, days 7, 14 and 21 prior to treatment; Cycle 2, days 1 and 21, prior to treatment. Samples will be collected for research banking at the following time points: Baseline, prior to treatment; Cycle 2, days 1 and 21, prior to treatment. See Section 14.0 for specific instructions.

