 5. Patient questionnaires will be completed at baseline (appendices IV and V only), Cycle 1 Day 14, Cycle 2 Day 1, Cycle 2 Day 14 and Cycle 2 Day 28. Cycle 2 Day 14 and Cycle 2 Day 28 patient questionnaire can be sent home with the patient to complete and return at their next clinic visit if needed. Patient questionnaire booklets **must** be used; copies are not acceptable for this submission.
 6. Performed at screening and then as needed.
 7. AST, ALT and total bilirubin will be checked at baseline and every other week during Cycles 1 and 2.
 8. +/- 1 day. Applies to days 1, 8, 15, and 22; includes baseline tests and procedures for Day 1 Cycle 1.
 9. If patient goes off study during Cycle 1 and last CT scan was done >28 days prior, the CT scan must be done.
 10. If a subject is on warfarin with stable PT/INR at baseline, the PT/INR should be assessed on Day 5 (+/- 3 days). If value is above the therapeutic range, the dose should be modified and the assessment should be repeated weekly until it is stable.
 11. Hematology and chemistry tests to be done prior to each cycle.
 12. If baseline history, exam, weight, ECOG PS, and blood pressure were performed ≤ 3 days of Cycle 1 Day 1, they do not need to be repeated for Cycle 1 Day 1.
 13. It is suggested that patients start treatment Tuesday-Friday to avoid PK collection on Sundays.
- R Research funded (see Section 19.0)

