Further description / examples of skin changes	Numbness, dysesthesia / paresthesia tingling, painless swelling, or erythema of the hands and/or feet	Painful erythema and swelling of the hands and/or feet	Moist desquamation, ulceration, blistering, or severe pain of the hands and/or feet
Effect on activities	Does not disrupt normal activities	Limiting instrumental activities of daily life (e.g., preparing meals, shopping for groceries or clothes, using the telephone, managing money)	Limiting self-care activities of daily life (e.g., bathing, dressing and undressing, feeding self, using the toilet, taking medications) and not bedridden
a. Palmer-plantar erythrodysesthesia syndrome is a disorder characterized by redness, marked discomfort, swelling, and tingling in the palms of hands or the soles of the feet.			

Grade of event (NCI-CTCAE v4.0)	Occurrence	Suggested Dose Modification
Grade 1	Any	Maintain dose level and immediately institute supportive measures for symptomatic relief
Grade 2	1 st occurrence	Consider decreasing dose by one dose level and immediately institute supportive measures. If no improvement, interrupt therapy for a minimum of 7 days, until toxicity resolves to Grade 0-1 ^{b,d}
	No improvement within 7 days or 2 nd occurrence	Interrupt therapy until toxicity resolves to Grade 0-1. When resuming treatment, treat at reduced dose level ^b
	3 rd occurrence	Interrupt therapy until toxicity resolves to Grade 0-1. When resuming treatment, decrease dose by one dose level. ^{b,d}
	4 th occurrence	Discontinue therapy
Grade 3	1 st occurrence	Institute supportive measures immediately. Interrupt therapy for a minimum of 7 days until toxicity resolves to Grade 0-1. ^c When resuming treatment, decrease dose by one dose level. ^{b,d}
	2 nd occurrence	Institute supportive measures immediately. Interrupt therapy for a minimum of 7 days until toxicity resolves to Grade 0-1. ^c When resuming treatment, decrease dose by one additional dose level. ^{b,d}
	3 rd occurrence	Discontinue treatment permanently.

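### HFS-14 has no pre-treatment score, so change from baseline, attribution of on-treatment scores and correction of chance imbalance are lost for this secondary endpoint

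*Combined protocol and SAP*

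**What the plan says.** Section 1.0 sets the HFS-14 times: "All patients will be required to fill HFS14 quality of life questionnaire on C1D14, C2D1, C2D14, and C2D28 intervals". Baseline is not among them. The Test Schedule lists three booklets, "Patient Questionnaire Booklets (Appendices IV, V, VI"), and footnote 5 restricts the first visit: "Patient questionnaires will be completed at baseline (appendices IV and V only), Cycle 1 Day 14".

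The appendices are not in the available text, so it is an inference that the omitted booklet is HFS-14. The inference is strong. Section 1.0 gives no baseline time for HFS-14, and Section 16.46 plans a change from baseline for LASA, which needs a LASA baseline.

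Exclusion 3.29p bars unresolved prior-therapy toxicity above grade 1, "excluding alopecia and oxaliplatin induced neurotoxicity" up to grade 2. The PPES grading table in Section 8.3 gives as grade 1 examples "Numbness, dysesthesia / paresthesia tingling, painless swelling, or erythema of the hands and/or feet". Section 1.2 describes HFS-14 as 14 questions "with three domains: hand, feet, and social".

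Goal 2.24 compares HFS-14 between dosing strategies and between PPES strategies. Section 16.46 does this with t-tests or Wilcoxon tests on the cycle 1 and 2 scores, within and between arms, and names no baseline term for HFS-14. It also hypothesizes greater deficits on regorafenib, as measured by HFS-14 among others.

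**The concern.** The first HFS-14 score is taken under treatment, in patients who may already have had numb or tingling hands and feet at entry. A poor score at C1D14 could therefore reflect early PPES, residual neuropathy or both, and nothing collected on the same scale separates them.

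At stake is the interpretation of the one patient-reported instrument aimed at PPES, in a trial that tests both a dosing strategy and a PPES strategy. A pre-treatment score cannot be recovered once dosing has begun.

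**Working it through.** **1. Can C1D14 serve as a baseline?** No. Section 1.1 places PPES onset in the first one to two weeks. By Day 14 the schedules in Sections 7.11 and 7.12 have given the two dosing arms different doses, and clobetasol in A1 and B1 has run since Day 1 (Section 6.22). The C1D14 score is already an outcome.

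**2. Does another item substitute?** Only in part. Section 10.51 requires a CTCAE grade for PPES at baseline, but neuropathy is not on that solicited list. Section 16.46 plans no HFS-14 adjustment for either. Neither is a stratification factor: Section 5.0 lists none and Section 6.21 names registering membership only.

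**3. Which comparisons are affected?**
- *Between arms.* Allocation is 1:1:1:1, so entry symptoms are balanced in expectation. What remains is variance and chance imbalance.
- *Within arms.* There is no pre-treatment value, so on-treatment scores cannot be set against a starting point.
- *The hypothesis of greater deficits on regorafenib.* Every arm receives regorafenib, so only a comparison with baseline could address it. For HFS-14 there is none.

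**4. The plan's own figure.** No sample size or power is stated for HFS-14. The only figure is 110 for the primary endpoint (45% vs 63%, one-sided alpha 0.20, power 80%, Fisher exact test). It reproduces: the continuity-corrected formula gives 54 per arm, 108 in total, and exact Fisher power at 55 per arm is 80.4%. HFS-14 does not enter this calculation.

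**5. Precision.** Adjusting for a baseline with correlation r to follow-up removes r² of the variance. The equivalent gain in patients is 1/(1 − r²) − 1. The documents give no r, so a range is shown. The last two columns assume 55 vs 55 (110/2, all forms completed) and two-sided 0.05. The difference detectable with 80% power is (1.960 + 0.842) × √(2/55) × √(1 − r²) SD.

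| r (assumed) | Variance removed | Equivalent extra patients | Detectable difference | Power for 0.5 SD |
|---|---|---|---|---|
| no baseline | – | – | 0.534 SD | 74.6% |
| 0.1 | 1% | 1/0.99 − 1 = 1% | 0.531 SD | 75.0% |
| 0.3 | 9% | 1/0.91 − 1 = 10% | 0.510 SD | 78.5% |
| 0.5 | 25% | 1/0.75 − 1 = 33% | 0.463 SD | 85.7% |

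**6. Chance imbalance.** If a share p of patients enters with neuropathy, the difference in prevalence between two groups of 55 has a 95% chance range of ±1.96 × √(2p(1 − p)/55). For p = 10% this is ±11 percentage points, and for p = 50% it is ±19. If neuropathy shifts the 0–100 score by 10 to 20 points, an imbalance at those limits moves the group difference by 0.112 × 10 = 1.1 points up to 0.187 × 20 = 3.7 points. Both p and the shift are assumptions.

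**The case against.** The strongest reply is randomization. A reader might infer that pre-existing neuropathy confounds the arm or clobetasol comparisons. The documents do not support that: allocation is random across all four arms, so the expected difference in entry symptoms is zero. This part of the reply stands in full.

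A reader might also infer that neuropathy is common at entry and moves HFS-14 substantially. The documents do not show this either. Criterion 3.13 requires progression on standard therapy but does not name oxaliplatin, and no prevalence is given. The symptom overlap is with the PPES grading table, not with HFS-14 items, which are not in the text. The overlapping symptoms are grade 1 examples that the table says do not disrupt normal activities. What the documents establish is that such symptoms are permitted, not how often they occur or how much they count.

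The precision gain may be small. All patients are regorafenib-naive (3.21), so a PPES-specific score could cluster near its best value at entry and correlate weakly with later scores. This is why the range starts at r = 0.1, where the gain is about 1%.

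Partial proxies exist: the baseline PPES grade, the history and exam, and the prior systemic therapy form (Section 18.1). They permit some adjustment but give no change score on the HFS-14 scale.

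Finally, HFS-14 is one instrument within a secondary goal, compared largely descriptively and without stated power. That limits the weight of the point but does not remove it.

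**Conclusion.** The point holds as a cheap improvement to a secondary endpoint. Without a pre-treatment HFS-14, the plan cannot compute change from baseline, set within-arm scores or the Section 16.46 hypothesis against a starting point, or correct a chance imbalance in entry symptoms. Between-arm comparisons remain free of systematic bias from entry symptoms, but are less precise than they could be.

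The loss is equivalent to about 1% to 33% of patients for this endpoint, conditional on the assumed correlation of 0.1 to 0.5. The conclusion also rests on the inference that Appendix VI is HFS-14.

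It would be wrong to read this as a threat to the primary result. The primary endpoint and N = 110 do not use HFS-14, and the grade 3 or 4 PPES comparison in Section 16.45 is much less affected because PPES is graded at baseline.

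**What to change.** - In footnote 5 of Section 4.0, add HFS-14 to the baseline booklet, and align the times in Section 1.0.
- In Section 16.46, compare HFS-14 between dosing arms and between PPES strategies adjusted for the baseline score, by ANCOVA or by a mixed model over the four on-treatment visits. The mixed model would also meet the stated intention to take time-dependence into account. Report change from baseline within each arm. Change within an arm remains a before-and-after description, not a randomized contrast.
- For patients already enrolled without a baseline form, adjust for baseline CTCAE PPES grade and any recorded neuropathy, and state the limitation in the report.

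The cost is one 14-item form at a visit where two questionnaires are already completed, a booklet reprint and a minor amendment. Sample size, eligibility and treatment do not change.

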5.0 Stratification Factors: None

6.0 Registration/Randomization Procedures

6.1 Randomization Procedures

- 6.11 To randomize a patient, access the ACCRU web page at [REDACTED] click on “Training Page” and enter the registration/randomization application. The registration/randomization application is available 24 hours a day, 7 days a week. Back up and/or system support contact information is available on the Web site. If unable to access the Web site, call the Academic and Community Cancer Research United (ACCRU) Registration Office at [REDACTED] between the hours of 8 a.m. and 4:30 p.m. Central Time (Monday through Friday).

The instructions for the registration/randomization application are available by using the Help button. Prior to initiation of protocol study intervention, this process must be completed in its entirety and an ACCRU subject ID number must be available as noted in the instructions. It is the responsibility of the individual and institution registering the patient to confirm the process has been successfully completed prior to release of the study agent. Patient registration via the registration/randomization application can be confirmed in any of the following ways:

- Contact the ACCRU Registration Office [REDACTED]. If the patient was fully registered, the ACCRU Registration Office staff can access the information from the centralized database and confirm the registration.
- Refer to “Instructions for Remote Registration” in section “Finding/Displaying Information about A Registered Subject.”

6.12 Correlative Research

- A mandatory correlative research component is part of this study. The patient will be automatically registered onto this component (see Sections 3.0 and 14.0).
- A mandatory banking component is part of this study. The patient will be automatically registered onto this component (see Sections 3.0 and 14.0).

- 6.13 Documentation of IRB approval must be on file in the Registration Office before an investigator may register any patients.

In addition to submitting initial IRB approval documents, ongoing IRB approval documentation must be on file (no less than annually) at the Registration Office ([REDACTED]). If the necessary documentation is not submitted in advance of attempting patient registration, the registration will not be accepted and the patient may not be enrolled in the protocol until the situation is resolved.

When the study has been permanently closed to patient enrollment, submission of annual IRB approvals to the Registration Office is no longer necessary.

- 6.14 Prior to accepting the registration/randomization, the registration/randomization application will verify the following:
- IRB approval at the registering institution
 - Patient eligibility
 - Existence of a signed consent form
 - Existence of a signed authorization for use and disclosure of protected health information
- 6.15 At the time of randomization, the following will be recorded:
- Patient has given permission for ACCRU to give his/her sample(s) to outside researchers.
- 6.16 Treatment cannot begin prior to randomization and must begin ≤ 7 days after randomization.
- 6.17 Pretreatment tests/procedures (see Section 4.0) must be completed within the guidelines specified on the test schedule.
- 6.18 All required baseline symptoms (see Section 10.5) must be documented and graded.
- 6.19a Treatment on this protocol must commence at an ACCRU institution under the supervision of a medical oncologist.
- 6.19b Blood draw kit is available on site.
- 6.19c Patient questionnaire booklet is available on site; copies are not acceptable for this submission.
- 6.2 Randomization Procedures
- 6.21 The registering membership will be used as the only stratification factor for this study.
- 6.22 After the patient has been registered into the study, the patient will be assigned to one of the following treatment groups, in 1:1:1:1 fashion, using the Pocock and Simon dynamic allocation procedure which balances the marginal distributions of the stratification factors between the treatment groups (Pocock-Simon, 1975).
- Arm A 1: Regorafenib Cycle 1: 80 mg daily Week 1/120 mg daily Week 2/160 mg daily week 3 then 1 week off followed by Cycle 2+ (160 mg for 21 days/1 week off) + pre-emptive strategy for PPES starting Cycle 1 Day 1
 - Arm A 2: Regorafenib Cycle 1: 80 mg daily week 1/120 mg daily week 2/160 mg daily week 3 then 1 week off followed by Cycle 2+ (160 mg for 21 days/then 1 week off) + reactive strategy for PPES
 - Arm B 1: Regorafenib 160 mg daily for 21 days/then 1 week off + pre-emptive strategy for PPES starting Cycle 1 Day 1
 - Arm B 2: Regorafenib 160 mg daily for 21 days/then 1 week off + reactive strategy for PPES

7.0 Protocol Treatment

7.1 Treatment Schedule

Arm	Agent	Dose	Route	Frequency	ReRx
A 1	Regorafenib	80 mg daily (Starting dose) See Section 7.11	PO	Daily for 21 days of 28 day cycle	Every 28 days
	Clobetasol (pre-emptive)	0.05% cream thin layer to palms and soles, avoid washing hands or feet for 1 hour after application	Topical	BID for first 12 weeks	BID for first 12 weeks starting Day 1 of regorafenib dose
A 2	Regorafenib	80 mg daily (Starting dose) See Section 7.11	PO	Daily for 21 days of 28 day cycle	Every 28 days
	Clobetasol (reactive)	0.05% cream thin layer to palms and soles, avoid washing hands or feet for 1 hour after application	Topical	BID (per physician discretion; recommend no longer than 12 weeks from initiation)	BID (per physician discretion upon occurrence of PPES Grade ≥ 1 ; recommend no longer than 12 weeks from initiation)
B 1	Regorafenib	160 mg (Starting dose)	PO	Daily for 21 days of 28 day cycle	Every 28 days
	Clobetasol (pre-emptive)	0.05% cream thin layer to palms and soles, avoid washing hands or feet for 1 hour after application	Topical	BID for first 12 weeks	BID for first 12 weeks starting Day 1 of regorafenib dose
B 2	Regorafenib	160 mg (Starting dose)	PO	Daily for 21 days of 28 day cycle	Every 28 days
	Clobetasol (reactive)	0.05% cream thin layer to palms and soles, avoid washing hands or feet for 1 hour after application	Topical	BID (per physician discretion; recommend no longer than 12 weeks from initiation)	BID (per physician discretion upon occurrence of PPES Grade ≥ 1 ; recommend no longer than 12 weeks from initiation)

Regorafenib tablets should be taken once a day with approximately 8 fluid ounces (240 mL) of water after a low-fat (<30% fat) meal. Regorafenib should be taken with a meal at the same time every day. Some examples of low fat meals are:

- Two slices of white toast with 1 tablespoon of low-fat margarine and 1 tablespoon of jelly and 8 ounces (240 mL) of skim milk (approximately 319 calories and 8.2 g of fat).

- One cup of cereal (i.e. Special K), 8 ounces (240 mL) of skim milk, one piece of toast with jam (no butter or marmalade), apple juice, and one cup of coffee or tea (2 g fat, 17 g protein, 93 g of carbohydrate, 520 calories).

